2.2 PRIMARY AND SECONDARY ENDPOINTS

2.2.1 Primary Endpoints

1. Incidence of early post-operative surgical site occurrences or wound related events (e.g. - ileus, deep or superficial wound infection, seroma, hematoma, wound dehiscence, skin necrosis, fistulae) noted at the hernia repair site and occurring within the first three months

of the ventral hernia repair.

2. Incidence of other early post-operative complications (e.g. ileus, bowel obstruction, fistula) occurring within the first three months of the ventral hernia repair.

2.2.2 Secondary Endpoints

- Incidence of late post-operative surgical site occurrences or wound related events (e.g. ileus, deep or superficial wound infection, seroma, hematoma, wound dehiscence, skin necrosis, fistulae, bulging) noted at the hernia repair site and occurring > 3 months after index surgery.
- 2. Incidence of other late post-operative complications (e.g. ileus, bowel obstruction, fistula) occurring > 3 months after index surgery.
- 3. Patient Reported Outcomes (QoL and pain assessments).
- 4. True hernia recurrence at the site of surgery at post-operative day 90 and 12 and 24 months.

2.3 STUDY DESIGN

This is a prospective, single arm, multi center, study evaluating the early post-operative clinical course and the true hernia recurrence rate of ventral hernias treated with the OviTex® Permanent 1S reinforced bioscaffold device. The study will be conducted at up to 7 sites and uses a prospective, observational design. Refer to Section 5 below for the Statistical Considerations of the study.

2.3.1 Rationale for the OviTex® Permanent 1S reinforced bioscaffold study

The purpose of the OviTex® Permanent 1S reinforced bioscaffold Study is to provide prospective data on the early post- operative clinical course and the true hernia recurrence rates in the repair of ventral hernias. Data relating to subjects with similar baseline characteristics will be correlated and compared to (prospective) published data where applicable.

2.4 NUMBER OF SITES/INVESTIGATORS

This study will be conducted at up to 7 investigational sites with [name]. serving as the Lead Principal Investigator.

2.5 NUMBER OF SUBJECTS

The study will enroll at least 100 subjects who complete the screening visit (see Section 5). Interim analyses will be performed to assess whether sufficient subjects exhibiting similar baseline characteristic have been included to allow statistical comparison to the literature. Based on the interim analyses enrollment may continue beyond 100 subjects.

2.6 STUDY ARMS

The study will include a single arm design with all subjects receiving the OviTex® Permanent 1S reinforced bioscaffold device.

2.7 INCLUSION CRITERIA

2.7.1 Inclusion Criteria at Screening: Visit 1

- Subject suffers from an uncomplicated ventral hernia that requires surgical repair (open, laparoscopic or robotic) with the use of an implant to reinforce or replace weakened or missing tissue.
- 2. The size of the implant needed for repair is expected to be 18 x 22 cm, 20 x 20 cm or less.
- 3. Subject meets CDC/SSI Wound Classification Class I (Clean), Class II (Clean-Contaminated) or Class III (Contaminated) criteria.
- 4. Subject is willing and able to sign an informed consent for the study and has signed the IRB approved Informed Consent form for this study.

- 5. Subject is able to complete Quality of Life (QoL) and pain Questionnaires.
- 6. Subject is at least 18 years old, (or considered an adult per state law).
- 7. Subject is able to participate fully in, and for the full duration of, the study.

2.8 EXCLUSION CRITERIA

2.8.1 Exclusion Criteria at Screening: Visit 1

- 1. Subject has a BMI of > 40
- 2. Subject meets CDC/SSI Wound Classification Class IV (Dirty-Infected) criteria
- 3. Subject is female and is pregnant.
- 4. Subject has a life expectancy of < 2 years making it unlikely that the subject will successfully achieve two-year follow-up.
- 5. Subject has recent history of drug or alcohol abuse (in last 3 years).
- 6. Subject has an allergy to ovine-derived products.
- 7. Subject has participated in another clinical trial within the past 30 days or is currently involved in another clinical trial.
- 8. Subject unable to receive OviTex® Permanent 1S reinforced bioscaffold at time of surgery

2.8.2 Exclusion Criteria Intraoperative: Visit 2

- 1. Subject requires implant that exceeds 18 x 22 cm or 20 x 20 cm.
- 2. Subject unable to receive OviTex® Permanent 1S reinforced bioscaffold at time of surgery.

3 STUDY PROCEDURES

3.1 BASELINE VISIT

The baseline visit will be performed in the 30 days prior to, including the day of, ventral hernia repair. Subjects will provide written consent, using the Institutional Review Board (IRB) approved informed consent form, before any study procedures are performed. After informed consent is obtained screening on all potential subjects will consist of the following:

- Assessment of subject's study eligibility according to study inclusion/exclusion
 criteria. Subjects who meet all of the inclusion and none of the exclusion criteria will
 be assigned a sequential subject number.
- A relevant physical examination including review of systems and collection of height, weight, BMI, blood pressure, temperature, as well as an abdominal examination to evaluate the ventral hernia and to estimate the defect size, (length, width, area cm²).
- A review of relevant medical history, including previous abdominal surgeries and any co-morbidities. A review of subject demographics including age, gender, race and ethnicity.
- Assessment of disease specific and general Quality of Life (QoL) surveys (HerQLes and EQ-5D), (See Appendix 1).
- A clinical evaluation to determine surgical approach (open, laparoscopic or robotic), a brief review of the surgical procedure and device to be used, in addition to preoperative instructions.

3.1.1 Surgical Date

Sites will notify TELA Bio of scheduled surgeries within 5 days of the actual surgery date to ensure that study product is on-site for the day of surgery.

3.1.2 Shipment of Study Device

The study will be performed using product that is provided at no cost by the Sponsor to all sites participating in the study.

3.2 SURGICAL VISIT

The surgical visit is split into three phases: admission, intraoperative and discharge.

3.2.1 Admission

During the admission visit, the following components will be collected/reviewed:

- A brief review of inclusion/exclusion criteria.
- An abbreviated review of subject's medical history to document any changes since the baseline visit.
- An abbreviated physical examination to evaluate hernia and document any changes since the baseline visit.
- Assessment of Surgical Site Infection (SSI) classification (See Appendix 2)
- For female subjects, a pregnancy test will be performed

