3.2.2 Intraoperative

On the day of surgery, definitive repair of the ventral hernia site will be performed with an OviTex® Permanent 1S reinforced bioscaffold implant. The Investigator will use the study product on a first-to-expire basis. Investigators will follow their individual Institutional guidelines for their standard surgical preparation regimen. During the index surgery, the following perioperative components will be collected:

- Type of approach (Laparoscopic versus Open)
- Actual size of defect (length, width, cm²)
- Product item and lot-serial number used

- Size of implant used in surgery (final mesh dimensions after any trimming)
- Location of implant (onlay, retrorectus, extraperitoneal, intraperitoneal or inlay/bridging)
- Operative data
 - o Component separation (anterior or posterior)
 - Fixation method (suture type and size)
 - o Number of drain(s) placed, drain volume and duration
 - Rectus muscle condition
 - o Presence or absence of adhesions
 - Any concomitant procedures
 - Iatrogenic injury
 - o Blood loss
 - Skin closure (complete restoration of abdominal wall and primary skin closure)
 - Operative time (time of first cut to last suture)
- All subjects will be assessed for intraoperative complications.
- Using a Likert scale, surgeons will be asked to provide their subjective assessment on the mesh handling characteristics as defined by ease of placement and ease of securing OviTex® Permanent 1S reinforced bioscaffold implant (See Appendix 3).

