7.2 STATISTICAL METHODS

Statistical methods will be carried out in accordance with the Statistical Analysis Plan (SAP) developed for this study.

The majority of data will be expressed as descriptive statistics. A p-value of less than or equal to 0.05 will be considered statistically significant. Any confidence bounds will show two-sided 95% confidence interval limits. Categorical variables will be summarized by number and percent. Continuous variables will be summarized by total number (N), mean, standard deviation, median, min and max. It is anticipated that the data will be evaluated using standard parametric and non-parametric procedures. Analyses of particular interest will be:

1. Correlation of rate of surgical site wound infection to SSI wound classification, number of previous repairs and pre-morbid conditions.

- 2. Correlation of surgical site occurrences or wound related events to re-herniation, BMI, number of previous abdominal.
- 3. Correlation of number of previous repairs with true hernia recurrence
- 4. Correlation of a visible bulge at hernia repair site with true hernia recurrence
- 5. Correlation of subject abdominal wall function and QoL with bulging at the hernia repair site and hernia recurrence rates.

The primary and secondary endpoints of this study will be also be compared to the clinical outcomes reported for other prospective studies in the literature. The results will be compared for the group as a whole, and, if the numbers will allow this, for subgroups of subjects exhibiting similar baseline characteristics, such as size of the hernia, co-morbid conditions, number of previous abdominal procedures etc.

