APPENDIX 2: SSI Wound Classification:

Classification	Criteria
Class I	Elective, not emergency, non-traumatic, primarily closed; no acute
Clean	inflammation, no break in technique; respiratory, gastrointestinal, biliary and genitourinary tracts not entered.
Class II	Urgent or emergency case that is otherwise clean; elective opening of
	respiratory, gastrointestinal, biliary or genitourinary tract with minimal spillage
Clean-	(e.g. appendectomy) not encountering infected urine or bile; minor technique
contaminated	break.
Class III	Non-purulent inflammation; gross spillage from gastrointestinal tract; entry
Contaminated	into biliary or genitourinary tract in the presence of infected bile or urine; major break in technique; penetrating trauma <4 hours old; chronic open wounds to be grafted or covered.
Class IV	Purulent inflammation (e.g. abscess); preoperative perforation of respiratory,
Dirty	gastrointestinal, biliary, or genitourinary tract; penetrating trauma >4 hours

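### Wound class is scheduled only before the operation, though Appendix 2 defines Classes I to III partly by operative events, so the infection-by-class analysis may use the wrong class for some subjects

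*Combined protocol and SAP*

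**What the plan says.** Section 3.2 sets the order of events: "The surgical visit is split into three phases: admission, intraoperative and discharge". Section 3.2.1 lists "Assessment of Surgical Site Infection (SSI) classification (See Appendix 2" under admission. Before that, wound class appears only as an eligibility condition at screening. Section 2.7.1 requires "Subject meets CDC/SSI Wound Classification Class I (Clean), Class II (Clean-Contaminated) or Class III (Contaminated) criteria", and Section 2.8.1 excludes Class IV.

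Appendix 2 defines the classes. Class I requires, among other things, "inflammation, no break in technique; respiratory, gastrointestinal, biliary and genitourinary tracts not entered". Class II includes elective opening of a "respiratory, gastrointestinal, biliary or genitourinary tract with minimal spillage", and a minor technique break. Class III includes "gross spillage from gastrointestinal tract" and a major technique break.

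Section 3.2.2 says "During the index surgery, the following perioperative components will be collected". Its list includes concomitant procedures and iatrogenic injury, and all subjects are assessed for intraoperative complications. Wound class is not on it, nor in the discharge and follow-up lists (Sections 3.2.3, 3.3 and 3.4).

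Section 7.2 names as its first analysis of particular interest "Correlation of rate of surgical site wound infection to SSI wound classification", together with number of previous repairs and pre-morbid conditions.

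**The concern.** A class assigned at admission can only anticipate whether a tract will be entered, whether contents will spill and whether technique will be broken. Take a subject who meets the Class I description at admission and then has an unplanned bowel injury with spillage. Appendix 2 would place that subject in a higher class. The plan provides no step that records the change and no rule for which class the analysis uses.

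At stake is the reading of the infection-by-class analysis. If contaminated operations are infected more often and are counted as clean, the clean-wound infection rate looks worse than it is and wound class looks less predictive. The same would apply to a literature comparison matched on wound class. Section 7.2 does not name class as a matching variable, although its list of examples is open-ended.

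**Working it through.** **Step 1: trace the variable through the protocol.**

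| Point in the study | Section | Wound class asked for? |
|---|---|---|
| Screening | 2.7.1, 2.8.1 | Yes, as eligibility |
| Admission | 3.2.1 | Yes |
| Operation | 3.2.2 | No |
| Intraoperative exclusions | 2.8.2 | No |
| Discharge, Day 30, Day 90, Months 12 and 24 | 3.2.3, 3.3, 3.4 | No |
| Analysis | 7.2 | Used; source not stated |

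**Step 2: sort the Appendix 2 criteria by when they can be known.**
- Usually knowable at admission: elective or urgent status, existing inflammation, chronic open wounds, trauma timing, preoperative perforation. A planned tract opening can be anticipated.
- Known only during or after the operation: unplanned tract entry, actual amount of spillage, minor or major break in technique.

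Only subjects whose class changes because of the second group, or whose planned tract entry does not take place, are affected.

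**Step 3: size.** The protocol has no figure to reproduce. Section 7.1 gives up to 100 subjects as a sample of convenience, with no rates or power. Every input below except the total of 100 and the 0.05 level (Section 7.2) is an assumption: 70 subjects truly Class I with 5% infection; 30 truly Class II-III with 20% infection; *k* of the 30 recorded as Class I; and recording error unrelated to infection within true class.

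Apparent Class I rate = (70 × 0.05 + *k* × 0.20) / (70 + *k*). Risk ratio = 0.20 / that rate.
- *k* = 0: 3.5/70 = 5.0%; risk ratio 4.0
- *k* = 3: 4.1/73 = 5.6%; risk ratio 3.6
- *k* = 10: 5.5/80 = 6.9%; risk ratio 2.9
- *k* = 15: 6.5/85 = 7.6%; risk ratio 2.6

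Exact power of a two-sided Fisher test at 0.05 is about 53%, 49%, 39% and 28% in the same order. It is calculated by summing the probabilities of all tables with p ≤ 0.05, with the recorded Class I count being the sum of two binomials.

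**Step 4: vary the assumptions.** Let the true Class II-III share be 20% to 40%, with 10% to 50% of that group recorded as Class I. At 5% versus 20% infection, the risk ratio falls from 4.0 to between 3.73 and 2.29. At 10% versus 30%, it falls from 3.0 to between 2.86 and 2.00. The contrast shrinks in every setting; by how much depends on the share misrecorded.

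**Step 5: the opposite error.** If instead 3 truly Class I subjects were recorded as Class II-III, the apparent Class II-III rate would be (30 × 0.20 + 3 × 0.05)/33 = 6.15/33 = 18.6%, and the risk ratio 18.6/5.0 = 3.7. This also weakens the association but leaves the Class I rate at 5.0%.

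**The case against.** The strongest reply is that nothing locks the admission class. The Time and Events Schedule marks inclusion and exclusion criteria on the Day of Surgery, and wound class is one of them. Section 3.2.2 records concomitant procedures, iatrogenic injury and complications, from which tract entry and bowel injury could largely be derived. The SAP to which Section 7.2 refers and the eCRF are not in the text reviewed, so a final-class field or derivation there cannot be ruled out. The analysis is also exploratory: Section 7.2 says most data will be descriptive, and there is no power target.

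Much of this stands, and it rules out several stronger readings that a reader might infer.
- *The class is fixed at admission.* The text does not forbid an update; it provides none.
- *All the criteria arise in the operation.* Several do not (Step 2).
- *The error runs only from higher class to lower.* A planned tract entry that is not performed runs the other way (Step 5).
- *Power collapses.* Misrecording of a third or more of Class II-III has no support in the documents. At 3 of 30 the loss is about 4 percentage points, and power is only about 53% with perfect classification under the 20% assumption.
- *The primary result is compromised.* Wound infection is part of primary endpoint 1, but that is a whole-cohort incidence that does not use wound class.

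What does not stand is that the collected data close the gap. No rule maps them to a class, and degree of spillage and technique breaks are not listed items. The eligibility check on the day of surgery is not said to yield an end-of-operation class. Without an instruction, sites could differ.

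**Conclusion.** The concern holds in limited form. As written, the last scheduled wound-class assessment precedes some of the events that define the class, and that class feeds a named analysis. Subjects with unplanned contamination would be analysed in too clean a class; over-classification is possible and is expected to be less frequent. The likely net effect is a raised apparent Class I infection rate and a weaker class-infection association, provided that higher classes are infected more often.

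The size is unknown, because the documents give no class mix, no infection rates and no frequency of intraoperative class change. Under the assumptions shown, the effect runs from modest (risk ratio 4.0 to 3.6 with 3 of 30 misrecorded) to substantial (4.0 to 2.6 with 15 of 30). The defect is confined to Section 7.2 analysis 1 and to any subgroup built on wound class. It is worth correcting because the correction is so cheap.

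**What to change.** 1. Add to the Section 3.2.2 list and the eCRF an item for the final CDC/SSI wound class at the end of the procedure, by Appendix 2. For subjects already treated, take it from the operative record where that record allows.
2. State in Section 7.2, and in the SAP it refers to, that analysis 1 uses this final class. Retain the admission class as well, so that changes between the two can be tabulated.
3. Separately, Class IV is an exclusion at screening in Section 2.8.1 but does not appear among the intraoperative exclusions in Section 2.8.2. The two passages must be reconciled so that the status of a subject found to meet Class IV at surgery is clear.

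The cost of items 1 and 2 is one field, one sentence and some record review for subjects already treated. Visits and sample size do not change.

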3.2.2 Intraoperative

On the day of surgery, definitive repair of the ventral hernia site will be performed with an OviTex® Permanent 1S reinforced bioscaffold implant. The Investigator will use the study product on a first-to-expire basis. Investigators will follow their individual Institutional guidelines for their standard surgical preparation regimen. During the index surgery, the following perioperative components will be collected:

- Type of approach (Laparoscopic versus Open)
- Actual size of defect (length, width, cm²)
- Product item and lot-serial number used

- Size of implant used in surgery (final mesh dimensions after any trimming)
- Location of implant (onlay, retrorectus, extraperitoneal, intraperitoneal or inlay/bridging)
- Operative data
 - o Component separation (anterior or posterior)
 - Fixation method (suture type and size)
 - o Number of drain(s) placed, drain volume and duration
 - Rectus muscle condition
 - o Presence or absence of adhesions
 - Any concomitant procedures
 - Iatrogenic injury
 - o Blood loss
 - Skin closure (complete restoration of abdominal wall and primary skin closure)
 - Operative time (time of first cut to last suture)
- All subjects will be assessed for intraoperative complications.
- Using a Likert scale, surgeons will be asked to provide their subjective assessment on the mesh handling characteristics as defined by ease of placement and ease of securing OviTex® Permanent 1S reinforced bioscaffold implant (See Appendix 3).

3.2.3 Discharge

On the day of hospital discharge, the following will be collected:

- Length of Stay, including number of days hospitalized prior to repair and following surgery, the number of days in ICU, step down and regular ward.
- Number of drains still in place, drain volume and duration.
- Any early surgical site occurrences (infections, seroma, hematoma, wound dehiscence)
 or wound related events noted at the hernia repair site.
- Any other early post-operative complications (ileus, fistulae).

3.3 POST-OPERATIVE DAYS 30 AND 90

At post-operative days 30 and 90, the following procedures will be completed:

- Number of drains still in place, drain volume and duration.
- Assessment of any surgical site occurrences or wound related events (infections, seromas, hematoma, wound dehiscence) noted at the hernia repair site.
- A relevant physical examination to evaluate hernia repair. If there is any suspicion of a recurrent hernia e.g. bulging noted at the repair site, an abdominal CT scan will be performed to confirm the clinical diagnosis. If it is determined that it is clinically necessary to repair the hernia recurrence during the study period, those subjects will complete their participation in the study at the time of that repair
- Assessment of any other post-operative complications (ileus, fistulae).
- Assessment of disease specific and general Quality of Life (QoL) surveys e.g. EQ-5D and HerQLes, (See Appendix 1).
- Subject and Surgeon satisfaction assessment of hernia repair (See Appendix 5).
- Subject assessment of post-operative pain as measured by the Pain Visual Analog Scale ((VAS) See Appendix 5).

3.4 POST-OPERATIVE MONTHS 12 AND 24

The following activities will be performed at months 12 and 24 of Study period visit:

- Assessment of any late surgical site occurrences or wound related events (e.g. infections, seromas, hematoma, wound dehiscence, bulging) noted at the hernia repair site.
- A relevant physical examination to evaluate hernia repair. If there is any suspicion of a recurrent hernia e.g. bulging noted at the repair site, an abdominal CT scan will be performed to confirm the clinical diagnosis. If it is determined that it is clinically necessary to repair the hernia recurrence during the study period, those subjects will complete their participation in the study at the time of that repair.

• Assessment of any other late post-operative complications (e.g. ileus, fistulae). Assessment of disease specific and general Quality of Life (QoL) surveys e.g. EQ-5D and HerQLes, (See Appendix 1).

- Subject and Surgeon satisfaction assessment of hernia repair (See Appendix 4).
- Subject assessment of post-operative pain as measured by the Pain Visual Analog Scale ((VAS) See Appendix 5).

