It is hypothesized that the use of OviTex® Permanent 1S reinforced bioscaffold in abdominal hernia repair (in comparable subjects) will result in less seroma formation, the same percentage or fewer infections and fewer surgical repair related secondary procedures such as fluid aspirations or wound debridement. In addition, the use of OviTex® Permanent 1S reinforced bioscaffold is expected to result in a similar or lower rate of true recurrent herniations as reported for comparable prospectively studied subjects in the literature treated with other implants. [30-33] Surgical procedure related outcomes tend to occur within the first three months after surgery, and the recurrence of a hernia may occur at any point in time after treatment. This study focuses on the surgical outcomes over the first 3 months and continues for a total of 24 months to capture the longer-term incidence of hernia recurrences.

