2 OBJECTIVES, HYPOTHESES, PRIMARY AND SECONDARY ENDPOINTS

2.1 OBJECTIVES

The study is designed to demonstrate that, in subjects with comparable characteristics, the use of OviTex® Permanent 1S reinforced bioscaffold in ventral hernias leads to the same or lower percentage of early post-operative complications and true hernia occurrences as compared to prospective reports in the literature for either synthetic or biological meshes.

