7.3 PLANNED ANALYSIS

Interim analyses will be performed to assess the short-term outcomes when the first 25, 50 and 75 active subjects reach 90 days. The final analysis for the primary endpoint will be performed when all active subjects have completed their 90-day follow-up, and when all subjects have completed their Month 12 visit. Additional analyses will be done when subjects have completed their 12 and 24 months visits.

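### Repair of a recurrence ends participation, but the protocol text gives no denominator or estimator for recurrence; a percentage among subjects still followed would understate it, chiefly at Month 24

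*Combined protocol and SAP*

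**What the plan says.** Sections 3.3 (Days 30 and 90) and 3.4 (Months 12 and 24) carry the same rule. A suspected recurrence is checked by CT, and if repair is judged clinically necessary, "those subjects will complete their participation in the study at the time of that repair".

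Section 2.2.2 lists the endpoint as "True hernia recurrence at the site of surgery at post-operative day 90 and 12 and 24 months". It does not say whether this means present at the visit or occurring by then.

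Section 7.2 states that "Categorical variables will be summarized by number and percent". It names no analysis set for recurrence, no time-to-event method and no handling of early exits, and it refers to an SAP whose text was not available for this review. On the later analyses, Section 7.3 says that "Additional analyses will be done when subjects have completed their 12 and 24 months visits".

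The result is meant for external comparison. The objective in Section 2.1 is to show that use of the device "leads to the same or lower percentage of early post-operative complications and true hernia occurrences as compared to prospective reports in the literature". Section 7.2 adds: "The primary and secondary endpoints of this study will be also be compared to the clinical outcomes reported for other prospective studies in the literature".

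Other wording points to a cumulative outcome. Section 1.2 says that follow-up "continues for a total of 24 months to capture the longer-term incidence of hernia recurrences", and Section 2.3 describes the study as "evaluating the early post-operative clinical course and the true hernia recurrence rate of ventral hernias treated with" the device.

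**The concern.** Exit under this rule is caused by the outcome being counted. A subject leaves because the hernia recurred and was repaired. If the Month 12 or Month 24 percentage is taken among subjects still followed, these failures vanish from it. The schedule has no visit between Day 90 and Month 12, or between Month 12 and Month 24, so a recurrence found and repaired in either gap could appear in no visit-based percentage at all.

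The study has one arm, so no concurrent control shares the distortion. The percentage is to be set against published ones, and an error in this direction would favour the claim of the same or less recurrence. The same variable also enters the correlation analyses in Section 7.2.

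**Working it through.** The plan states no expected recurrence rate, margin or power, so there is no figure of its own to reproduce. The question is what the same data would show under the definitions that the wording allows.

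**Inputs.** N = 100 implanted, taken from the planned size in Section 7.1. R = 10 or 20 recurrences by Month 24 is an illustration; both lie inside the 2.7% to 62% range quoted in Section 1.1. The share repaired before the Month 24 visit is not in the documents; 30%, 50% and 80% are assumed, giving k repaired subjects. In this first step nobody is lost for another reason.

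**Three definitions.**
- (a) Among subjects still followed: (R − k)/(N − k)
- (b) Cumulative over all implanted: R/N
- (c) Cumulative numerator, followed-only denominator: R/(N − k)

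| R | k | (a) | (b) | (c) |
|---|---|---|---|---|
| 10 | 3 | 7/97 = 7.2% | 10.0% | 10/97 = 10.3% |
| 10 | 5 | 5/95 = 5.3% | 10.0% | 10/95 = 10.5% |
| 10 | 8 | 2/92 = 2.2% | 10.0% | 10/92 = 10.9% |
| 20 | 6 | 14/94 = 14.9% | 20.0% | 20/94 = 21.3% |
| 20 | 10 | 10/90 = 11.1% | 20.0% | 20/90 = 22.2% |
| 20 | 16 | 4/84 = 4.8% | 20.0% | 20/84 = 23.8% |

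**Direction.** (b) minus (a) equals k(N − R)/[N(N − k)], which is positive whenever k > 0 and R < N. For R = 10 and k = 5 it is 5 × 90/(100 × 95) = 4.7 percentage points. The exact 95% intervals are 4.9% to 17.6% for 10/100 and 1.7% to 11.9% for 5/95. Under (c) the error is smaller and goes the other way.

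**By visit.** The table concerns Month 24. At Month 12 only repairs done before that visit can leave the count, so the effect is smaller. A recurrence first found at a visit is counted at that visit even under (a).

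**Loss for other reasons.** This is separate from the exit rule, and it decides whether a plain count under (b) is enough. Assume constant rates over 24 months: h = −ln(1 − p)/24 for recurrence with true risk p, and c = −ln(1 − L)/24 for unrelated loss L. The share of implanted subjects with an observed recurrence is h/(h + c) × [1 − (1 − p)(1 − L)].
- p = 10%: L = 10% gives 0.5 × (1 − 0.81) = 9.5%; L = 20% gives 9.0%; L = 30% gives 0.228 × (1 − 0.63) = 8.4%.
- p = 20%: 19.0%, 18.0% and 16.9% for the same losses.

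A plain count over all implanted subjects therefore removes the exit-rule error but still reads low when follow-up is incomplete.

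**The case against.** The strongest reply is that nothing in the document calls for definition (a). Number and percent is silent on the denominator. The Section 7.3 sentence on completed visits says when analyses run, not who is in them. The lean is the other way: the synopsis speaks of re-herniations after use of the device, Section 1.2 of longer-term incidence, Section 2.3 of a recurrence rate, and the Section 7.2 correlations treat recurrence as an outcome per subject. Repaired recurrences would be in the database in any case, because Section 6.3.1 has recurrence noted as an adverse event and Section 4 has surgeries recorded. Denominators are also ordinary SAP content.

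All of that stands. A reader might infer that the plan commits to visit completers and will understate recurrence. The documents do not show this; understatement from the exit rule is possible, not established. The size is not fixed either, since the repair shares are assumed and the most striking figures come from the highest share.

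It can also be said that a time-to-event estimate is a matter of taste in a mainly descriptive convenience sample, and that visit windows blur event times. The windows are a real difficulty, and the fix deals with them. The preference for a time-to-event estimate does not rest on the exit rule alone: with ordinary loss, the plain count is low under every assumption shown.

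**Conclusion.** The point holds as a conditional one and should be fixed. The protocol text pairs an outcome-dependent exit with a percentage whose denominator it does not state. With 10 recurrences in 100, half of them repaired before Month 24, the admissible definitions give 5.3%, 10.0% or 10.5% from the same data. Unrelated loss of 10% to 30% would lower a plain count from a true 10% to between 9.5% and 8.4%. These figures rest on the assumed repair shares, constant rates and 100 implanted subjects.

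The scope is one secondary endpoint: mainly the Month 24 rate, less so the Month 12 rate. A reader might extend the criticism to the exit rule itself or to the 90-day primary endpoints; this point supports neither. If the SAP already defines the denominator and handles loss, a cross-reference would close the matter.

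**What to change.** In Sections 2.2.2 and 7.2 (and the SAP):
- Define recurrence as cumulative incidence from surgery through Day 90, Month 12 and Month 24 in all implanted subjects. Name that set explicitly, because Section 2.5 counts subjects at screening and Section 2.8.2 allows exclusion during surgery.
- Count every CT-confirmed or repaired recurrence as an event that stays counted at all later time points. Never treat repair as censoring.
- Estimate by Kaplan-Meier, or Aalen-Johansen with death as a competing event, with a two-sided 95% confidence interval, and show the plain n/N alongside. State the assumption that other losses are unrelated to recurrence.
- Read the estimate at the upper end of each visit window (2 weeks after Day 90, 4 weeks after Months 12 and 24), so that recurrences found at an in-window visit are included. Treat a subject seen without recurrence at an in-window Month 24 visit as followed to that limit; otherwise the risk set thins out artificially inside the window.

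Leave the exit rule and the timing triggers in Section 7.3 unchanged. Reporting, at each visit, how many subjects had left for repair alongside the quality-of-life and pain results would be useful but is optional.

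The cost is a few sentences and slightly more analysis work. No new data are needed, since CT checks, adverse events and surgeries are already collected. The stated recurrence rate may be less favourable than a percentage at the visit.
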